The tDCS device was a Phoresor-II Auto (Model PM850, Iomed, Salt Lake City Utah, USA). Participants were randomized to receive real or sham tDCS. For real tDCS, the device was ramped to 2 mA and maintained this current for 20 minutes. For sham tDCS, the device was ramped to 2 mA, but after 30 seconds, was ramped back down to 0 mA and stayed off for the remainder of the 20 minutes. During stimulation, participants rated the painfulness and unpleasantness of any scalp sensations using numeric rating scales (e.g., 0=no pain to 10=worst pain imaginable). Ratings were collected at stimulation onset, 5-minutes, 10-minutes, 15-minutes, and during the last 30-seconds of stimulation). Further, verbal descriptors of all scalp sensations, pain-related or otherwise, were recorded as well as all adverse events associated with the study. At the end of the study, participants were asked to guess whether they received real or sham tDCS. Further, they were asked to rate their confidence in their guess (0=completely guessing to 10=absolutely sure).

Participants rated the scalp pain associated with real tDCS as 1.98 (SD=2.02) out of 10 on average while those receiving sham tDCS rated their scalp pain as 0.18 (SD=0.27). These means are both low considering the 11-point range of the NRS, but they were significantly different ($t(22)=2.94$, $p=.008$). Participants receiving real tDCS rated the unpleasantness of the scalp sensations as 3.34 (SD=2.44) out of 10 on average whereas those receiving sham rated the unpleasantness as 0.43 (SD=0.49) on average ($t(22)=3.88$, $p=.001$). The scalp painfulness and unpleasantness ratings associated with real tDCS decreased over time during stimulation. Despite the between group differences in stimulation painfulness and unpleasantness, participants were not able to correctly guess whether they received real or sham stimulation at a rate better than chance ($X^2(1)=2.10$, $p=.21$, ns). In the real stimulation group, 46% of participants guessed correctly ($X^2=.004$, $p=.94$, ns) and in the sham group 18% guessed correctly ($X^2(1)=2.23$, $p=.14$, ns). The average guess-confidence rating was 5.50 (SD=3.10) in the real tDCS group and 4.55 (SD=2.16) in the sham group ($t(22)=0.86$, $p=.399$, ns).

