Overall, we have found that stimulating pain-modulating areas of the human cortex can significantly reduce post-operative opioid requirements without negatively impacting subjective pain ratings, and in some cases, it can significantly decrease pain ratings even though patients use less opioids. Further, we observe large effect-sizes for 20-minutes of TMS and for 80-minutes of tDCS. The investigators have demonstrated the feasibility of, and expertise for conducting brain stimulation in the post-operative setting and these promising, preliminary findings of novel brain stimulation technologies suggest that future studies are warranted. The field of minimally-invasive brain stimulation for pain is expanding rapidly, but it is still in its infancy. tDCS appears to have the potential to serve as an adjunct to post-operative pain management strategies, but more studies are needed in this area employing larger-scale, well-controlled clinical trial designs to evaluate the specificity of tDCS dosing strategies and to begin to elucidate possible mechanisms of action.

D. RESEARCH DESIGN AND METHODS (including data analysis)

Figure 1. Study overview and patient flow

Overview: The proposed study employs a randomized, double-blind, sham-controlled design to evaluate the effects of tDCS on pain among veterans receiving unilateral TKA or unilateral THA. Further, this study will examine dose-dependency of the tDCS analgesic effects. 120 patients undergoing TKA will be randomly assigned to one of four groups: *Group1*- 4-sessions of real tDCS, *Group2*- 2-sessions of real tDCS (+ 2 sham-sessions), *Group3*- 1-session of real tDCS (+ 3 sham-sessions), or *Group4*- 4-sessions of sham tDCS. Participants' PCA opioid pump usage will be tracked and pain and mood ratings will be collected (see figure 1). Follow-up ratings and opioid use data will be collected at 1, 3 and 6-months post-op.

Participants: Participants will be 120 patients undergoing TKA or THA surgery at the Ralph H. Johnson VAMC in Charleston SC. Inclusion/Exclusion criteria are as follows:

- 1) Between the ages of 25 and 90
- 2) No implanted medical devices above the waist
- 3) Mentally capable of reading, writing, giving consent, and following instructions
- 4) Not pregnant
- 5) Cleared for and scheduled for unilateral TKA or THAsurgery
- 6) No history of seizures
- 7) Not allergic to latex rubber

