PATIENT CONTROLLED ANALGESIA (PCA) PUMP USAGE: After tDCS administration, patients will be started on a patient controlled analgesia (PCA) pump. For statistical analyses of PCA pump usage, morphine-equivalent analgesic dose will be calculated (e.g., 0.2 mg of hydromorphone = 1.0 mg of morphine). Initial PCA settings will consist of hydromorphone 0.2mg/dose with a lockout interval of 10 minutes. The 4-hour maximum dose will be 4.8mgs with no continuous infusion. If a patient does not tolerate hydromorphone, the PCA medication can be changed to a different opioid and morphine-equivalent dosing will be used. If pain is not adequately controlled, the patient will be reassessed by

study personnel prior to increasing the PCA dosing regimen. PCA pump usage will be downloaded from the PCA pump after discharge from the hospital.

MEDICAL OUTCOMES STUDY SHORT-FORM 36 HEALTH SURVEY (SF-36) is a 36-item measure of general health intended to capture quality of life, functional ability and well-being (mental and physical). The SF-36 will be administered pre-surgery, at discharge, 3-month and 6-month follow-up.

BEST GUESS QUESTIONNAIRE will be used to determine how accurately patients, raters and tDCS operators were able to assess which treatment the patient received. This will assess our success in masking the sham treatments. Any time a guess-confidence rating is greater than 8 (on a 0 to 10 numeric rating scale), the PI will follow-up with the participant and/or administrator in order to determine what factors contributed to this level confidence. If the guess is verified correct by the statistical support personnel and any valid systematic administrative factors are identified (e.g., the participant or tDCS administrator reports that the he/she overheard the device-masking assistant discussing the device configuration, accidentally viewed the randomization codes, or felt/heard some unique tDCS-induced sensations that led them to correctly guess the condition), the participant will remain enrolled in the study (and no feedback will be provided to the administrator or participant regarding whether the guess was correct in order to avoid providing information that may further jeopardize the blind in later subjects). The participant's data will be dropped from analyses and steps will be taken to correct the mask procedure.

Table 1. Overview of the measurement schedule for the proposed study (POD=post-operative day)

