Statistical Analysis and Power: The orthopaedic surgeons at the Ralph H. Johnson VAMC conduct ~100 unilateral total knee arthroplasties and ~50 unilateral total hip arthroplasties each year . Thus, in order to meet the proposed n-size of the current study, 24 (out of 100) participants will need to be eligible and interested in participating in the trial each year. We will over recruit to permit for drop-outs and participants lost to follow-up. For analysis of primary outcomes associated with Aim-1, participants receiving any active tDCS (groups 1,2 & 3) will be collapsed and compared to the sham-only group. Multivariate multiple regression will be used with group-assignment entered into the model as a binary predictor. Surgery and anesthesia duration, depression & anxiety scores, sex, age, pre-tDCS pain, (ROM) Means and pre-op chronic opioid status will be entered into the model as covariates to permit for statistical control of these potentially confounding variables. Overall differences between real and

sham tDCS groups will then be examined for our primary outcomes: total post-op PCA morphine-equivalent dose, VAS pain-on-average ratings, and mean number of post-operative complications. Using the most conservative effect-size estimate from our series of pilot studies ($d=.70$), with 90 patients in the active tDCS group and 30 in the active-sham group, power is good to detect significant effects if they exist ($\alpha=.016$ (corrected for multiple DV's); $1-\beta >.80$; see figure 9). For Aim-2, MANCOVA will be conducted using all 4 groups and all primary dependent measures in the same model (controlling for surgery and anesthesia duration, depression & anxiety scores, pre-tDCS pain, physical rehab measures and chronic opioid status). With four groups of 30 patients each, assuming a moderate effect size $f^2(V)=.2$, and alpha of .05, power is good detect significant main effects in the model ($1-\beta >.80$). Secondary analyses will be conducted to evaluate long-term effects of tDCS on pain, functioning and quality of life (i.e., 2-wk, 4-wk, 8-wk, 3-month and 6 month-follow-up).

Problems/Challenges/Potential Pitfalls: The proposed tDCS device is an FDA-approved iontophoresis device, and its use for tDCS applications is off-label. The tDCS procedure is minimal-risk and FDA-

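### Dropping patients whose confident guess proves correct makes exclusion depend on the true allocation and can unbalance the arms

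*Combined protocol and SAP*

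**What the plan says.** The rule is in Section D, Dependent Measures, under the Best Guess Questionnaire. Patients, raters and tDCS operators guess the treatment and rate their confidence from 0 to 10. A rating above 8 leads the PI to follow up with the participant or the administrator. The condition for exclusion reads: "If the guess is verified correct by the statistical support personnel and any valid systematic administrative factors are identified". The examples of such factors are an overheard device configuration, sight of the randomisation codes, or that the person "felt/heard some unique tDCS-induced sensations that led them to correctly guess the condition". The patient stays enrolled, but "The participant's data will be dropped from analyses and steps will be taken to correct the mask procedure".

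Statistical Analysis and Power (Section D) pools groups 1 to 3 (90 patients) against sham (30 patients). It names no all-randomised analysis set and no analysis that restores the excluded patients. On attrition it says only: "We will over recruit to permit for drop-outs and participants lost to follow-up".

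Section C (Motor Cortex tDCS Laboratory Pain Pilot) gives the only data on guessing. "Participants receiving real tDCS rated the unpleasantness of the scalp sensations as 3.34 (SD=2.44) out of 10 on average", against 0.43 for sham. Correct guesses were 46% in the real group and 18% in the sham group, but "participants were not able to correctly guess whether they received real or sham stimulation at a rate better than chance" (p=.21). "The average guess-confidence rating was 5.50 (SD=3.10) in the real tDCS group and 4.55 (SD=2.16) in the sham group" (p=.399).

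**The concern.** This is a planned exclusion after randomisation of patients who were treated and followed. It is neither withdrawal nor missing data. Two patients can be equally sure of their guess and have the same reason for it, yet the one who is right is removed and the one who is wrong is kept. Membership of the analysis set is thus a function of the true allocation.

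One of the qualifying causes is itself a consequence of treatment. Active current runs for 20 minutes, while sham current is switched off after 45 s (Blind Maintenance), so the sensations can differ by arm. If patients who feel the stimulation strongly also differ in opioid need, removing more of them from one arm biases the comparison of PCA use.

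Two features widen the problem. An administrator's guess can remove a patient whose own blind was intact. Groups 2 and 3 receive both real and sham sessions, and the documents do not say what a correct guess is for them, so removal can also differ between the dose groups that Aim 2 compares.

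**Working it through.** **Inputs.** From Statistical Analysis and Power: 90 active, 30 sham, d=.70, alpha=.016 (two-sided assumed, since the plan does not say). From the pilot in Section C: correct guesses 46% and 18%; confidence 5.50 (SD 3.10) real and 4.55 (SD 2.16) sham.

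**The plan's own power.** Noncentrality is .70 × √(90 × 30/120) = 3.32. The noncentral t with 118 df gives power .808 (normal approximation .819). The stated value above .80 is reproduced.

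**Removal rates.** Assumptions: the pilot figures carry over, confidence is normal and independent of correctness, and every confident correct guess is traced to a cause.

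- P(confidence > 8), real: 1 − Φ((8 − 5.50)/3.10) = .210
- P(confidence > 8), sham: 1 − Φ((8 − 4.55)/2.16) = .055
- Removed, active: .210 × .46 = .097, or 8.7 of 90
- Removed, sham: .055 × .18 = .010, or 0.3 of 30

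Removals caused by administrators' guesses are not counted.

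**Bias and type I error.** Let sensitivity to sensations S and opioid use Y be standard normal with correlation r, with no true treatment effect. The documents give no r, so a range is used. Results are from 200,000 simulated trials per setting, with an unadjusted pooled t test at two-sided .016. Negative bias means lower apparent opioid use in the active arm.

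(A) The most sensitive patients are removed: the top .097 of active and the top .010 of sham.

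| r | Bias (SD) | Type I error |
|---|---|---|
| 0 | 0.000 | .0160 |
| .2 | −0.034 | .0176 |
| .3 | −0.049 | .0190 |
| .5 | −0.082 | .0261 |
| −.5 | +0.081 | .0254 |

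(B) Weaker selection: S decides who exceeds 8, and those patients are removed at random with probability .46 (active) or .18 (sham).

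| r | Bias (SD) | Type I error |
|---|---|---|
| .2 | −0.025 | .0169 |
| .3 | −0.038 | .0178 |
| .5 | −0.064 | .0213 |
| −.5 | +0.064 | .0219 |

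**Fewer guesses traced.** Under the same two models with r of .2 to .5, the bias is 0.012 to 0.046 SD (type I error .016 to .018) if half are traced. It is 0.006 to 0.025 SD (.016 to .017) if a quarter are traced.

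**Loss of numbers only (r = 0).** With 81 active and 30 sham, noncentrality is .70 × √(81 × 30/111) = 3.28 and power is .795, before any over-recruitment.

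**A harsher case, for range.** Suppose 20% of active and 10% of sham are removed, and removal depends directly on the outcome: low users in active and high users in sham, with a logit slope of 0.5 to 1.0 per SD. The bias is then 0.15 to 0.26 SD against tDCS, and type I error is .042 to .114. Neither these rates nor this selection pattern comes from the documents.

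**The case against.** The case for leaving the rule alone, or treating it as minor, has real content.

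- The pilot does not show that sensations lead people to the right answer. If the guess was binary, 82% of sham and only 46% of real participants guessed real. The 46% versus 18% contrast also appears to be the very comparison reported with p=.21: taking 6/13 and 2/11 (arm sizes inferred) gives chi-square 2.098, against 2.10 in the protocol. With 24 people, the two rates are poorly known. **This stands** and limits any claim about size.
- The pilot used healthy volunteers and a 30 s sham, and this protocol allows topical benzocaine for strong skin sensations. Any gap between arms could be narrower here. **This stands.**
- Full tracing is close to an upper case for patients' own guesses. If ratings are whole numbers, a cut at 8.5 gives 7.7% and 0.6% removed instead of 9.7% and 1.0%. The normal model also puts about 7% of real-arm ratings above the scale maximum of 10. With the planned covariates, r should be read as a partial correlation, which may be smaller. **These stand.**
- PCA use and VAS pain are under the patient's control, so keeping a patient known to be unblinded admits expectation bias. The worry is legitimate, but the rule does not remove it: patients who guessed correctly with confidence of 8 or less stay in. A sensitivity analysis without the flagged patients shows the same information without giving up the randomised comparison.

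None of this changes the fact that exclusion is decided by checking the guess against the allocation, or that no planned analysis restores these patients.

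**Conclusion.** The concern holds. Followed as written, the plan does not compare the groups as randomised. Its direction cannot be determined from the documents: a positive correlation between sensitivity and opioid use favours tDCS, and a negative one favours sham.

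On the pilot-based assumptions with full tracing, the size is modest: a false difference of 0.03 to 0.08 SD and type I error of .017 to .026 against .016. It may be smaller, or nil if those removed do not differ in opioid need. In that case the only cost is about one percentage point of power, which over-recruitment may cover. Confidence in the defect is high; confidence in its size is low, because neither the removal rate nor the correlation is given. It should be fixed, since the fault is certain and the remedy nearly free.

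**What to change.** In the Best Guess Questionnaire text, replace the exclusion with: *All randomised participants are analysed in the group to which they were randomised, whatever their guess.* State the same analysis set in Statistical Analysis and Power.

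Report guess accuracy, confidence and the number of patients meeting the rule for each of the four groups, after defining a correct guess for groups 2 and 3. Repeat the analysis without the flagged patients only as a labelled sensitivity analysis. Keep the step that corrects the masking procedure.

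The cost is one sentence in the protocol and one summary table by group, with no extra data or patients.

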tDCS Electrode

Placement: All participants will have an EEG 10-20 cap placed F3 will be marked with a non-toxic felt-tipped pen. The tDCS anode will be placed over the mark (see figure 8) and the cathode will be placed over the right dorsolateral prefrontal cortex (F4). Electrodes will be held in place with Velcro straps.

tDCS Methods: tDCS will be delivered in four 20-minute-sessions (100 minutes total)

[figure not shown]
and will be conducted with the Phoresor-II Auto (Model PM850, Iomed, Salt Lake City Utah, USA) using 2mA current. This constant current device ramps up to the desired amplitude to minimize discomfort for participants and ramps the amplitude back to 0mA at the end of the programmed treatment duration. Electrodes will be standard small (4cm X 4cm) sponge electrodes soaked in a sterile solution of 0.9% sodium chloride insulated by a latex casing. The current density and total charge delivered by the above parameters is consistent with those used safely in the current research literature on tDCS. A very low dose (0.125mL) of topical benzocaine (6%) cream may be applied to the skin beneath the sponge electrodes for ~10 minutes and then removed if the participant experiences strong cutaneous sensations (patient report) during stimulation. After stimulation, a vitamin-E/Aloe cream will be applied to the skin under the electrodes following each treatment to reduce risks associated with skin drying.

tDCS Dosing: Custom-developed software will be used to generate random number sequences and save them in a file-format readable by the tDCS blinding software. Participants will be randomized to one of four groups in order to assess the effects of total tDCS charge on post-operative pain.

Group1 will receive a total of four 20-minute sessions of active 2mA tDCS (2 sessions on post-op day 0; and 2 sessions on post-op day 1)

Group2: will receive a total of two 20-minute sessions of active 2mA tDCS (2 sessions on post-op day 0; and 0 sessions on post-op day1) followed by 2 sessions of sham tDCS (both on post-op day 1).

Figure 8. Trajectory of anodal stimulation associated with the proposed tDCS electrode placement strategy

Group3: will receive a only one 20-minute session of active tDCS on post-op day 0, followed by three sessions of sham tDCS (1 on post-op day 0 and 3 on post-op day 1).

Group4: will receive a total of four 20-minute sessions of sham tDCS (2 sessions on post-op day 0; and 2 sessions on post-op day 1)

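### Knee and hip patients are both enrolled and procedure type is to be recorded for statistical control, but joint is in neither the Aim-1 nor the Aim-2 model

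*Combined protocol and SAP*

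**What the plan says.** **Population.** Section D, Participants: "Participants will be 120 patients undergoing TKA or THA surgery". Section D, Statistical Analysis and Power gives annual surgical volumes of roughly "100 unilateral total knee arthroplasties and ~50 unilateral total hip arthroplasties each year".

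**Intention to control.** Section D, Anesthesia/Surgical Measures and Procedures names knee and hip arthroplasty as the eligible operations. It then says that procedure type and device manufacturer will be recorded so that their influence on post-operative pain can be controlled in the analysis.

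**Models.** Section D, Statistical Analysis and Power lists the covariates.
- Aim 1: surgery and anaesthesia duration, depression and anxiety scores, sex, age, pain before stimulation, range-of-motion means, and pre-operative chronic opioid status.
- Aim 2: surgery and anaesthesia duration, depression and anxiety scores, pain before stimulation, physical rehabilitation measures, and chronic opioid status.

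Neither list contains joint or procedure type.

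**Allocation.** Section D, tDCS Dosing: "Custom-developed software will be used to generate random number sequences and save them in a file-format readable by the tDCS blinding software", and "Participants will be randomized to one of four groups in order to assess the effects of total tDCS charge on post-operative pain". Procedures and Flow adds that the study ID is linked to a randomisation file. No ratio, block scheme or stratification factor is stated. The power statements assume fixed sizes: "with 90 patients in the active tDCS group and 30 in the active-sham group, power is good to detect significant effects if they exist" for Aim 1 and "With four groups of 30 patients each" for Aim 2.

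**The concern.** The protocol treats the kind of operation as something that can affect post-operative pain and arranges to record it for that reason, but the analysis section does not use it. The primary comparison sets 90 pooled active patients against 30 sham patients, so a few hips more or fewer in the sham arm moves its case mix noticeably.

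If knee and hip patients differ in opioid use or pain, two things follow. In any one realised trial, a chance imbalance in joint shifts the estimated effect and the written model does not correct it. Whether or not there is an imbalance, the knee/hip difference inflates the residual variance, which costs precision. Section B gives grounds for expecting procedures to differ: it argues for working out analgesia procedure by procedure and justifies a knee-only focus. The total-knee pilot in Section C enrolled knee patients only.

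**Working it through.** **1. The plan's own figure.** Inputs from Statistical Analysis and Power: 90 active against 30 sham, d = 0.70, alpha = .016. Sidedness is not stated; two-sided is assumed.

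Noncentrality = 0.70 × √(30 × 90 / 120) = 0.70 × 4.743 = 3.320, on 118 degrees of freedom. Noncentral-t power = **.808**, which agrees with the stated value above .80. With nine degrees of freedom removed for covariates it is .807, and with ten (one more for joint) it is still .807. The added covariate therefore costs essentially nothing in degrees of freedom.

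**2. Chance of a knee/hip imbalance.** Assumption: enrolment follows surgical volume, so the hip share is 50/150 = 1/3, or 40 hips in 120. Sham is fixed at 30 and allocation is not stratified by joint.

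The number of sham hips X is hypergeometric (120 patients, 40 hips, 30 drawn), with mean 10. The gap in hip share is

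|X/30 − (40 − X)/90| = 4|X − 10|/90,

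so it moves in steps of 4.4 points.

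| Gap at least | Sham hips | Smallest attainable gap | Probability |
|---|---|---|---|
| 10 points | ≤7 or ≥13 | 13.3 points | .263 |
| 15 points | ≤6 or ≥14 | 17.8 points | .116 |
| 20 points | ≤5 or ≥15 | 22.2 points | .043 |

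The hip share is an assumption. By the same formula, 30 hips in 120 gives .33 and .14 for the first two rows, and 50 hips gives .39 and .20.

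**3. What an imbalance would do to the estimate.** The documents give no knee/hip difference in opioid use. For illustration, take an assumed difference of 0.5 to 1.0 SD. The shift is gap × difference.

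- At a gap of 13.3 points: 0.067 to 0.133 SD, or 10% to 19% of d = 0.70.
- At a gap of 17.8 points: 0.089 to 0.178 SD, or 13% to 25% of d = 0.70.

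For scale, the standard error of the contrast is √(1/30 + 1/90) = 0.211 SD.

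**4. Precision.** With a hip share of 1/3, joint accounts for (1/3)(2/3) × difference² of the outcome variance. At 0.5 SD this is 0.222 × 0.25 = 5.6%; at 1.0 SD it is 22.2%. If no other covariate captures it, adjusting for joint reduces the standard error from 0.211 to 0.211 × √0.944 = 0.205, or to 0.211 × √0.778 = 0.186.

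**5. Allocation scheme (secondary).** Suppose allocation were unrestricted at 1:1:1:1. The sham size would be Binomial(120, .25), with mean 30, SD 4.74 and a 95% range of 21 to 40. Power by sham size would be .680 at 21, .748 at 25, .798 at 29, .808 at 30, .849 at 35 and .877 at 40. Averaged over the distribution it is **.799**. The chance of 25 or fewer sham patients is .17.

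**The case against.** **The plan already foresees control for procedure.** This is true, and it rules out saying that the plan ignores the issue. However, the commitment stops at recording, and both covariate lists are written as complete. One could also read procedure type as surgical technique (cemented or cementless, computer-assisted or conventional) rather than joint. On that narrower reading, joint is not provided for anywhere, so the gap is wider.

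**Other covariates carry part of the difference.** Surgery duration, pain before stimulation and chronic opioid status may absorb some of it. That is plausible and makes the figures in steps 3 and 4 upper values for a given raw difference. It is not a reason to omit a factor that is already recorded.

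**Chance imbalance does not invalidate a randomised test.** This stands. Over repeated randomisations the imbalance is part of the error that the standard error describes. The case for adjustment rests on precision and on the accuracy of the one trial that is run, not on a broken type I error rate.

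**A stronger inference about randomisation.** A reader might infer that the sequences are simple and unblocked, so that the design cannot deliver 30 per arm and the power claim fails. The documents do not support this. They are silent on blocks, a pre-generated sequence can be blocked, and "With four groups of 30 patients each, assuming a moderate effect size" is consistent with planned equal allocation. Nor would the consequence be large: average power falls by about one point, and a sham arm above 30 raises it. One could say that unrestricted allocation gives a 46% chance of power below .80, but that is only the probability of 29 or fewer sham patients, and power at 29 is .798. The plan also intends to over-recruit, although this raises the total without controlling the split.

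**Conclusion.** The omission of joint from both models is documented and sits awkwardly with the plan's stated reason for recording procedure type. Assuming 40 hips in 120 and 30 sham patients, there is a 26% chance of a hip-share gap of at least 10 points and a 12% chance of at least 15, with no adjustment in the written models. How much that matters depends on the knee/hip difference in opioid use and pain, which the documents do not give. At an assumed 0.5 to 1.0 SD, a gap of 17.8 points moves the estimate by 0.09 to 0.18 SD. This is a worthwhile improvement at almost no cost, not a flaw that undermines the trial.

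The unspecified allocation scheme is a matter of missing detail. No failure to reach 30 per arm can be concluded from it.

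**What to change.** Add joint (knee or hip) as a covariate in the Aim-1 regression and the Aim-2 MANCOVA in Statistical Analysis and Power, and say there that this is how the recorded procedure type will be used. If procedure type was meant to cover technique as well, state which of those variables enter the models. The cost is one degree of freedom for joint; no new data and no extra patients are needed.

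As a clarification, state the allocation ratio, whether blocks are used, and any strata under tDCS Dosing. If the file is not already blocked, generate it with permuted blocks before use, optionally stratified by joint. Blocks of four in two strata would hold the sham arm at 29 to 31 of 120 (recomputed power .798 to .818) and nearly equalise hip share. The cost is regenerating the file and managing two lists. Covariate adjustment alone deals with the knee/hip point if stratification is not wanted.
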